6.1 Study treatment

6.1.1 Investigational and control drugs

The study treatment consists of:

- Investigational drug
 - Hydroxychloroquine (HCQ): doses of 200 mg or placebo
 - Azithromycin (AZI): dose of 250 mg or placebo

Table 6-1 Investigational and control drug

Investigational/ Control Drug	Pharmaceutical Dosage Form	Route of Administration	Supply Type	Sponsor (global or local)
HCQ 200 mg	Tablet	Oral use	Open label	Sponsor global
HCQ Placebo	Tablet	Oral use	Open label	Sponsor global
AZI 250 mg	Tablet	Oral use	Open label	Sponsor global
AZI Placebo	Tablet	Oral use	Open label	Sponsor global

6.1.2 Treatment arms/group

Participants will be assigned at Day 1 to one of the following 3 treatment arms in a ratio of 1:1:1. The treatment arms include:

Arm 1: hydroxychloroquine (HCQ) plus azithromycin (AZI) placebo

- HCQ: 600mg o.d. as loading dose (Day 1) followed by 200 mg t.i.d. The time between the 600mg loading dose and first 200mg dose should be 8-hours (not to exceed 12 hours)
- AZI placebo o.d. The loading dose of AZI placebo (Day 1) should be taken 4 hours after loading dose of HCQ

Arm 2: hydroxychloroquine (HCQ) plus azithromycin (AZI)

- HCQ: 600 mg o.d. as a loading dose (Day 1) followed by 200 mg t.i.d.. The time between the 600mg loading dose and first 200mg dose should be 8-hours (not to exceed 12 hours)
- AZI: 500 mg as a loading dose (Day 1) followed by 250 mg o.d. Day 2 – Day 5. The 500mg loading dose of AZI (Day 1) should be taken 4 hours after loading dose of HCQ

Arm 3: hydroxychloroquine (HCQ) placebo plus azithromycin (AZI) placebo

- HCQ placebo o.d. (Day 1) followed by HCQ placebo t.i.d. The time between the first and the second dose should be 8 hours (not to exceed 12 hours) to match other treatment arms.
- AZI placebo o.d. The loading dose of AZI placebo (Day 1) should be taken 4 hours after loading dose of HCQ placebo

6.1.3 Treatment duration

The total treatment duration of hydroxychloroquine is 10 days. The approach to include a loading dose on Day 1 is preferred in order to rapidly reach higher target tissue drug concentrations. The total treatment duration of azithromycin will be 5 days.

In case a participant is discharged prior to Day 10, they may complete study treatment as planned, at home, until Day 10 if QTcF \leq 480 ms at the time of discharge based on the local ECG data. Otherwise, treatment will be discontinued at the time of discharge.

6.2 Other treatment(s)

6.2.1 Concomitant therapy

All relevant medications, procedures, and significant non-drug therapies (e.g. blood transfusions) administered after the participant was enrolled into the study must be recorded on the appropriate Case Report Forms (CRFs).

6.2.1.1 Standard of care for COVID-19 disease

All participants will receive best standard of care as background therapy. Although there are no specific therapies approved for the treatment of COVID-19, participants with moderate and severe disease are expected to receive supportive care as dictated by local treatment guidelines. Depending on the disease severity, supportive care may include the use of oxygen supplementation, antibiotic prophylaxis and other concomitant medications for comorbidities, ventilator support, and intensive care management for disease progression.

The study permits any of standard of care for COVID-19 disease except the medications listed in the prohibited medication in [Table 6-2](#).

6.2.2 Rescue medication

Rescue therapy may be used at the discretion of the Investigator if there is evidence of clinical deterioration of COVID-19 disease and intervention with a rescue therapy is required beyond the standard of care measures.

6.2.3 Prohibited medication

Table 6-2 Prohibited medication

Medication	Prohibition period
Any drug known to prolong QTc interval (See https://crediblemeds.org/ for details as well as protocol supplementary guidance)	Within 5 half-lives before screening and throughout the study
Antiviral agents e.g. remdesivir, oseltamivir, interferon, lopinavir/ ritonavir or other protease inhibitors, chloroquine, nitazoxanide, convalescent COVID19 serum or anti-SARS-COV-2 immunoglobulins	Up to Day 15 or until discharge whichever earlier Except in the case these are needed to be used as rescue therapy (see Section 6.2.2)
Newly approved COVID-19 therapies (if any available since issuing the protocol)	Within 5 half-lives or 30 days of screening whichever is longer, and up to Day 15 or until discharge whichever earlier. Except in the case these are needed to be used as rescue therapy (see Section 6.2.2)

6.3 Participant numbering, treatment assignment, randomization

6.3.1 Participant numbering

Each participant is identified in the study by a Participant Number (Participant No.), that is assigned when the participant is enrolled for screening and is retained for the participant throughout his/her participation in the trial. A new Participant No. will be assigned at every subsequent enrollment if the participant is re-screened. The Participant No. consists of the Center Number (Center No.) (as assigned by Novartis to the investigative site) with a sequential participant number suffixed to it, so that each participant's participation is numbered uniquely across the entire database. Upon signing the informed consent form, the participant is assigned to the next sequential Participant No. available.

Participant numbers are assigned when the site creates the first entry for the participant in the CRF, therefore CRF entry must be created prior to contacting the Interactive Response Technology system.

6.3.2 Treatment assignment, randomization

At Day 1, all eligible participants will be randomized via Interactive Response Technology (IRT) to one of the treatment arms. The unblinded pharmacist will contact the IRT after confirmation from the investigator or his/her delegate that the participant fulfills all the inclusion/exclusion criteria. The IRT will assign a randomization number to the participant, which will be used to link the participant to a treatment arm and the unblinded pharmacist will be provided with the treatment arm assigned to the participant.

The randomization numbers will be generated using the following procedure to ensure that treatment assignment is unbiased and concealed from participants and investigator staff. A participant randomization list will be produced by the IRT provider using a validated system

that automates the random assignment of participant numbers to randomization numbers. These randomization numbers are linked to the different treatment arms.

The randomization scheme for participants will be reviewed and approved by a member of the Randomization Office.

The unblinded pharmacist MUST NOT communicate the information of treatment arm to anyone who is involved to the study (site personnel including the investigator, participant, sponsor). If accidentally communicated to anyone, Novartis local monitor should be notified and the study treatment should be discontinued.

6.4 Treatment blinding

The study will be double-blind as both Investigator and participants will be blinded to the study medication from the time of randomization until the final database is locked after the last follow-up visit at Day 40.

Open label supply of investigational treatments (HCQ and AZI) and similar appearance placebo will be provided at site to the unblinded site pharmacist.

Unblinding will occur in the case of participant emergencies and will only be undertaken by the investigator (See [Section 6.5.2](#)). The unblinded pharmacist is not involved in emergency unblinding.

Designated Novartis clinical trial team members will be unblinded following data extraction for the primary endpoint analysis (Day 15) to perform the analysis.

Other Novartis team members, Investigators and participants will remain blinded to individual treatment allocation until final database lock. In addition, for the purposes of the Data Monitoring Committee (DMC) analysis, there will be unblinded Independent Statisticians and Programmers in charge of DMC reporting activities.

6.5 Additional treatment guidance

6.5.1 Treatment compliance

The unblinded pharmacist must record all study treatment dispensed in the Drug Accountability Log, which must not be shared with blinded members of the site staff.

The site staff must record the date and time of dosing for each medication in the source documents for the participant.

In the case that a participant is discharged prior to Day 10, they should be instructed on the dosing requirements and contacted at Day 10 to confirm compliance. The participant must also be instructed to contact the investigator if he/she is unable for any reason to take the study treatment as prescribed.

Compliance will be assessed by the investigator and/or study personnel at each visit using the information provided by the participant. This information should be captured in the source documents.

6.5.2 Emergency breaking of assigned treatment code

Emergency code breaks must only be undertaken when it is required to in order to treat the participant safely. Blinding codes may also be broken after a participant discontinues treatment due to disease progression if deemed essential to allow the investigator to select the participant's next treatment regimen, and after discussion and agreement with the sponsor. Most often, study treatment discontinuation and knowledge of the possible treatment assignments are sufficient to treat a study participant who presents with an emergency condition. Emergency treatment code breaks are performed using the IRT. When the investigator contacts the system to break a treatment code for a participant, he/she must provide the requested participant identifying information and confirm the necessity to break the treatment code for the participant. The investigator will then receive details of the investigational drug treatment for the specified participant and a fax or email confirming this information. The system will automatically inform the Novartis monitor for the site and the study team that the code has been broken.

It is the investigator's responsibility to ensure that there is a dependable procedure in place to allow access to the IRT/code break cards at any time in case of emergency. The investigator will provide:

- protocol number
- name
- participant number

In addition, oral and written information must be provided to the participant on how to contact his/her backup in cases of emergency, or when he/she is unavailable, to ensure that un-blinding can be performed at any time.

6.6 Preparation and dispensation

Each study site will be supplied with study drug in packaging as described under investigational and control drugs section.

As per the treatment assigned to the participant, the unblinded pharmacist will select the study treatment to be dispensed to the participant.

6.6.1 Handling of study treatment and additional treatment

6.6.1.1 Handling of study treatment

In order to ensure treatment blinding study treatment must be received, stored in a secure location and dispensed only by an unblinded pharmacist. All study treatment must be stored according to the instructions specified on the labels.

Clinical supplies are to be dispensed only in accordance with the protocol. Technical complaints are to be reported to the respective Novartis Country Organization Quality Assurance.

Medication labels will be in the local language and comply with the legal requirements of each country. They will include storage conditions for the study treatment but no information about the participant except for the medication number.

An accurate record of the shipment and dispensing of study treatment should be maintained in a drug accountability log. Monitoring of drug accountability will be performed by monitors during site visits or remotely and at the completion of the trial.

At the conclusion of the study, and as appropriate during the course of the study, the investigator will return all unused study treatment, packaging, drug labels, and a copy of the completed drug accountability log to the Novartis monitor or to the Novartis address provided in the investigator folder at each site.

7 Informed consent procedures

Eligible participants may only be included in the study after providing (witnessed, where required by law or regulation), IRB/IEC-approved informed consent.

If applicable, in cases where the participant's representative(s) gives consent (if allowed according to local requirements), the participant must be informed about the study to the extent possible given his/her understanding. If the participant is capable of doing so, he/she must indicate agreement by personally signing and dating the written informed consent document.

Informed consent must be obtained before conducting any study-specific procedures (e.g. all of the procedures described in the protocol). The process of obtaining informed consent must be documented in the participant source documents.

Novartis will provide to investigators in a separate document a proposed informed consent form that complies with the ICH GCP guidelines and regulatory requirements and is considered appropriate for this study. Any changes to the proposed consent form suggested by the investigator must be agreed by Novartis before submission to the IRB/IEC.

Information about common side effects already known about the investigational drugs can be found in the USPI/applicable labelling information. This information will be included in the participant informed consent and should be discussed with the participant during the study as needed. Any new information regarding the safety profile of the investigational drugs that is identified between labelling updates will be communicated as appropriate, for example, via an investigator notification or an aggregate safety finding. New information might require an update to the informed consent and then must be discussed with the participant.

The following informed consents are included in this study:

- Main study consent, which also includes:
 - A subsection that requires a separate signature for the 'Optional Consent for Additional Research' to allow future research on data/samples collected during this study
- As applicable, Pregnancy Outcomes Reporting Consent for female subjects or the female partners of any male subjects who took study treatment

Women of child bearing potential must be informed that taking the study treatment may involve unknown risks to the fetus if pregnancy were to occur during the study and agree that in order to participate in the study they must adhere to the contraception requirements.

Male participants must be informed that if a female partner becomes pregnant while he is enrolled in the study, contact with the female partner will be attempted to request her consent to collect pregnancy outcome information.

A copy of the approved version of all consent forms must be provided to Novartis after IRB/IEC approval.

8 Visit schedule and assessments

The Assessment Schedule ([Table 8-1](#)) lists all of the assessments when they are performed. All data obtained from these assessments must be supported in the participant's source documentation.

Participants should be seen for all visits/assessments as outlined in the assessment schedule ([Table 8-1](#)) or as close to the designated day/time as possible. Missed or rescheduled visits should not lead to automatic discontinuation.

Table 8-1 Assessment schedule

Period	Screening	Treatment						Post treatment		Unscheduled ¹ (report assessments as applicable)
Visit Name	Screening	Day 1	Day 2	Day 4	Day 6	Day 8	Day 10/ early discharge	Day 15 / early withdrawal Primary Endpoint	End of study follow up	
Days	-3 to 0	1	2	4	6	8	10	15	40	-
Informed consent	X									
Inclusion / Exclusion criteria	X	X								
Demography	X									
Medical history/current medical conditions	X									
Chest imaging	X ³							X ³		
Randomization		X								
Drug dispensation and administration					X					
Pregnancy test (serum and urine dipstick)	X									
Physical Examination, vital signs and body measurements ²	X	X	X	X	X	X	X			X
SARS-COV-2 test	X ⁴	X			X		X			X
Electrocardiogram (ECG)	X	X ⁵	X	X	X ⁶		X ⁶			X
Laboratory assessments (hematology, chemistry, urinalysis, ██████████) ⁷	X			X			X	X ³		
Biomarker plasma and serum		X					X	X		
Prior and concomitant medications							X			
Adverse Events							X			
Study completion information							X			

X Assessment to be recorded in the clinical database or received electronically from a vendor, ¹ All assessments for unscheduled visits are optional, ²Height and weight collected at screening only, ³ If available record findings, ⁴ If results of a previously performed test within 4 days prior to planned randomization are available this does not need to be repeated for screening ⁵ pre-dose and 4 hours post dose, ⁶ If required in the opinion of the Investigator. ⁷Hematology: Hct, Hgb, PLT, RBC, WBC, differential WBC count; Chemistry: ALP, ALT, AST, Ca, Mg, K, creatinine, direct and total bilirubin, BUN, glucose, troponin (I or C), CPK, ██████████

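### Section 6.6.1.1 has the blinded investigator return the drug accountability log to the monitor, which contradicts the protocol's own blinding rules

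*Protocol*

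**What the plan says.** All four products are listed as open label in Protocol Table 6-1, and section 6.4 describes the arrangement: "Open label supply of investigational treatments (HCQ and AZI) and similar appearance placebo will be provided at site to the unblinded site pharmacist". The blind is therefore kept by procedure at the site. The relevant rules are:

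- Section 6.4: "both Investigator and participants will be blinded to the study medication from the time of randomization until the final database is locked". Sponsor staff other than those designated for the Day 15 analysis also stay blinded to individual allocation until that lock.
- Section 6.6.1.1, opening: "study treatment must be received, stored in a secure location and dispensed only by an unblinded pharmacist". Protecting the blind is the stated reason.
- Section 6.5.1: the pharmacist records what is dispensed in the "Drug Accountability Log, which must not be shared with blinded members of the site staff".
- Section 6.3.2: "The unblinded pharmacist MUST NOT communicate the information of treatment arm to anyone who is involved to the study". The text names the investigator and other site personnel, the participant and the sponsor.

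The last paragraph of section 6.6.1.1 then says that "the investigator will return all unused study treatment, packaging, drug labels, and a copy of the completed drug accountability log to the Novartis monitor"; a sponsor address is the alternative. The instruction applies at the conclusion of the study and, as appropriate, during it. The same section adds: "Monitoring of drug accountability will be performed by monitors during site visits or remotely and at the completion of the trial".

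**The concern.** Because the supply is open label, the separation between the pharmacist and everyone else is what keeps allocation concealed at the site. The return instruction puts the investigator on the wrong side of that separation, and the log goes on to a monitor whom no section describes as unblinded.

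The blind has work to do in this trial. Section 4.1 gives reduction of bias in evaluating clinical response as a reason for the double-blind design. Readiness for discharge is a route to primary response, and where discharge is held up administratively its date depends on the investigator's opinion (8.3.1). Rescue therapy is at the investigator's discretion (6.2.2). An investigator who knew a participant's arm could be influenced on either.

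**Working it through.** No arithmetic applies: the plan states no figure on this point, and the question is whether the instructions can be followed together. Taking them in turn:

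1. **Who is blinded.** The investigator, from randomization to final lock after Day 40 (6.4).
2. **Who may handle the drug.** Only the unblinded pharmacist may receive, store and dispense it (6.6.1.1). Return is not in that list.
3. **Who may see the log.** Not blinded site staff (6.5.1). By step 1 the investigator is one of them.
4. **Who returns the log.** The investigator (6.6.1.1). To return a copy, the investigator must be given one, which step 3 forbids.
5. **When.** At the conclusion of the study and, as appropriate, during it. The first time point is not tied to database lock and the second falls before it, so the conflict can arise while step 1 still applies.
6. **Who receives it.** The monitor, or a sponsor address. Section 11.3 has the field monitor check participant records and data entry as well as drug accounting. Section 6.4 allows unblinding of designated staff for the Day 15 analysis and of independent statisticians and programmers serving the data monitoring committee. It makes no such provision for monitors. Section 6.3.2 bars arm information from the sponsor. Sending the log to the address instead of the monitor does not alter step 4.
7. **Whether another passage resolves it.** No protocol section assigns the return to the pharmacist, defers it to lock or names an unblinded monitor. The SAP has no text on drug accountability, drug return or an unblinded monitor.

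The returned items do not carry equal risk. Unused stock and packaging show what was not dispensed, and labels carry no participant information apart from a medication number (6.6.1.1). Neither need reveal an individual's arm. The log records dispensing, so it is the item that could link a participant to a product. The protocol does not show the log's layout; that it identifies participants is an inference, supported by the ban in 6.5.1. The contradiction between steps 3 and 4 does not depend on that inference.

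**The case against.** The best defence is that naming the investigator is site-responsibility wording. The section opens by giving handling to the unblinded pharmacist, section 6.5.1 gives that pharmacist the log, and a sensible site would let the pharmacist do the return. The log is described as completed and the conclusion of the study comes first, so a mid-study handover covering participants still under assessment is not required. This reading is possible, but the protocol does not state it, and return during the study is expressly allowed. On the sponsor side, the monitor's blinding status is unstated and section 11.3 refers to a monitoring plan that is not among the documents. That half is a gap to be reconciled with 6.3.2 and 6.4; it does not show that a blinded monitor would receive the log.

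A reader might infer more than the documents support:

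- **That knowing past assignments reveals current ones from the tablets.** Section 6.4 says the placebo looks similar, and section 6.1.2 gives every arm both components, active or placebo.
- **That the return would trigger treatment stops under 6.3.2.** That rule concerns accidental communication of the arm. Treatment lasts at most 10 days, and unused drug would normally come back after dosing has ended.
- **That participants discharged early take home an identifying pack.** Section 6.6 says "Each study site will be supplied with study drug in packaging as described under investigational and control drugs section" and that the pharmacist selects what to dispense. It is silent on the dispensing container, and silence is not an instruction to hand over the open-label pack.
- **That the Type I error is inflated by some amount.** Any figure would need an assumed shift in judged response, and nothing in the documents ties such a shift to log return. The SAP also plans counts and percentages for the primary endpoint (2.5.2) and no statistical models (5.4), so the reduced analysis has no primary test whose error rate could be inflated.

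**Conclusion.** The return instruction is wrong as written. It contradicts section 6.5.1 directly, and it conflicts with 6.4 and 6.3.2 because it places a record of dispensing with a blinded investigator and then with sponsor staff not described as unblinded. It is a general instruction, so it applies at every site. How many allocations it would disclose, and with what bias, cannot be derived from the documents.

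Two things limit its weight. The disclosure risk lies mainly in the log, and only in a handover before final lock. The SAP (sections 1 and 1.1) reports that the study was halted on 19 June 2020 with 20 participants randomized, one of them mis-randomized, against about 444 planned. The practical effect is therefore small, but the contradiction remains. The documents do not show that the blind was broken, or that following the plan must break it.

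**What to change.** In section 6.6.1.1, make the unblinded pharmacist, instead of the investigator, the person who returns unused treatment, packaging, labels and the copy of the log. In the same section, adopt one of two rules for the receiving side. Either the log and open-label packs are reviewed and received only by unblinded sponsor personnel who do not monitor that site's clinical data, or they are handed over only after final database lock. Align the sentence on accountability monitoring and the field monitor's duties in section 11.3 with the rule chosen, so that 6.3.2, 6.4, 6.5.1 and 6.6.1.1 agree.

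The cost is protocol wording. The unblinded pharmacist role already exists. The small downside is that drug reconciliation is routed to other personnel or, under the second rule, deferred until after lock.
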